| 16 | Presentation of data and timeframe..... | 19 |
| 17 | Key-references | 20 |

1 List of abbreviations

| | |
|-------|--|
| AE | Adverse event |
| AMI | Acute myocardial infarction |
| ARNi | Angiotensin receptor – neprilysin inhibition |
| CI | Cardiac index |
| EF | Ejection fraction |
| LV | Left ventricular |
| PCWP | Pulmonary capillary wedge pressure |
| SAE | Serious adverse event |
| SUSAR | Suspected unexpected severe adverse reaction |

2 Synopsis

| Drug Name | LCZ696, Valsartan/sacubitril (Entresto) | | | | | | | | | | | | | | | | | | | | |
|---|--|--------------------------------------|--------------------------------------|--------------------------------------|--------------------------------------|-------------|-------|-----|-----|-------------|-------|-----|-----|-------------|-------|-----------|-----|------------|-------|----|-----|
| Study Design | A Prospective, multicenter, randomized (1:1) double blind controlled trial of the LCZ696 versus placebo. | | | | | | | | | | | | | | | | | | | | |
| Objective | The main objective of this study is to assess the effect of angiotensin–neprilysin inhibition on central hemodynamics, myocardial structure and myocardial function in patients with a recent AMI and Doppler echocardiographic signs of diastolic dysfunction and preserved systolic function. | | | | | | | | | | | | | | | | | | | | |
| Study Hypothesis | LCZ696 will compared with placebo improve central hemodynamics, reduce pulmonary capillary wedge pressure (PCWP), and increase cardiac index (CI) during exercise in patients with diastolic dysfunction after AMI. A beneficial effect that is attributed to improved cardiac remodeling (attenuation of cardiac fibrosis). | | | | | | | | | | | | | | | | | | | | |
| Number of Subjects | 100 total subjects. | | | | | | | | | | | | | | | | | | | | |
| Primary Endpoint and Measurement | The primary endpoint will be the ratio of mean PCWP at peak exercise divided by cardiac index at peak exercise. | | | | | | | | | | | | | | | | | | | | |
| Secondary Endpoints | Amount of hyperenhancement on cardiac MRI; ST2 concentration at rest; Left atrial volume by echocardiography and left atrial emptying fraction by echocardiography at rest; MR-proANP and NT-proBNP concentration. | | | | | | | | | | | | | | | | | | | | |
| Study Population | A total of 100 male or nonpregnant females aged ≥ 50 years with a recent documented AMI, diastolic dysfunction, and LVEF $\geq 45\%$ on echocardiography performed within 72 hours of the AMI will be enrolled at selected invasive centers in Denmark. | | | | | | | | | | | | | | | | | | | | |
| Sample Size Considerations | 
Based on previous data it is expected that PCWP will increase to 32 ± 8 mmHg and cardiac index to 7.4 ± 1.4 l/min/m², with a PCWP/CI ratio of 4.49 ± 1.4. To detect a decrease of 20% in primary endpoint with alpha of 0.05 and beta 0.8, a total of 90 patients are required, to allow 10% dropout rate 100 patients are expected to be enrolled.
 
  
 Difference in PCWP/CI ratio	Standardized difference	N (Total) $\alpha=0.05/\beta=0.8$	N (Total) $\alpha=0.05/\beta=0.9$	
   
 10% (0.449)	0.299	320	450	
 
 15% (0.674)	0.449	150	200	
 
 20% (0.898)	0.598	90	110	
 
 25% (1.12)	0.748	70	100	
  
 | Difference in PCWP/CI ratio | Standardized difference | N (Total) $\alpha=0.05/\beta=0.8$ | N (Total) $\alpha=0.05/\beta=0.9$ | 10% (0.449) | 0.299 | 320 | 450 | 15% (0.674) | 0.449 | 150 | 200 | 20% (0.898) | 0.598 | 90 | 110 | 25% (1.12) | 0.748 | 70 | 100 |
| Difference in PCWP/CI ratio | Standardized difference | N (Total) $\alpha=0.05/\beta=0.8$ | N (Total) $\alpha=0.05/\beta=0.9$ | | | | | | | | | | | | | | | | | | |
| 10% (0.449) | 0.299 | 320 | 450 | | | | | | | | | | | | | | | | | | |
| 15% (0.674) | 0.449 | 150 | 200 | | | | | | | | | | | | | | | | | | |
| 20% (0.898) | 0.598 | 90 | 110 | | | | | | | | | | | | | | | | | | |
| 25% (1.12) | 0.748 | 70 | 100 | | | | | | | | | | | | | | | | | | |
| Inclusion Criteria | 
 1. Documented ST segment elevation or non ST- myocardial infarction according to current guidelines 2. Complete revascularization 3. Age ≥ 50 years 4. LVEF $\geq 45\%$ on echocardiography performed within 72 hours of the MI. 5. Diastolic dysfunction defined as: Ratio of early diastolic peak mitral inflow velocity (E) to early mitral annulus diastolic velocity (e') ratio > 8 and at least moderate LA dilatation (LA volume index > 34 mL/m²). 6. Signed informed consent | | | | | | | | | | | | | | | | | | | | |
| Exclusion Criteria | 
 1. Intolerance towards study medication 2. Permanent atrial fibrillation, 3. Known history of cardiomyopathy, 4. More than mild valvular heart disease, 5. Severe obstructive or restrictive pulmonary disease, 6. Inability to perform exercise testing, 7. Inadequate acoustic windows on echocardiography, | | | | | | | | | | | | | | | | | | | | |

| | |
|---|--|
| | 
 8. Ongoing treatment with an angiotensin converting enzyme inhibitor at randomization. 9. Class I indication for an angiotensin converting enzyme inhibitor 10. Symptomatic hypotension, a systolic blood pressure of less than 100 mm Hg at screening 11. An estimated glomerular filtration rate (eGFR) below 30 ml per minute per 1.73 m² of body-surface area at any time, 12. A serum potassium level of more than 5.2 mmol per liter at screening, 13. A history of hereditary or idiopathic angioedema or unacceptable side effects during receipt of angiotensin converting enzyme inhibitor or angiotensin receptor blocker 14. Inability to provide informed consent 15. Concomitant use of drugs containing aliskiren in patients with diabetes mellitus. 16. Severe reduced liver function, biliary cirrhosis or cholestasis (Child-Pugh class C) 17. Pregnant or nursing(lactating) women(see section 8.2.1 for details) 18. Fertile women unless they are using a highly effective method of contraception(see section 8.2.2 for details) |
| Estimated Start Date, Enrollment Phase and tracking plan | 
Study start is expected to be June 2018, with an estimated enrollment phase of 2 years. Patients will be enrolled during hospitalization for AMI. Before randomization, spirometry, blood testing, comprehensive resting Doppler echocardiography, resting right heart catheterization, 6-minute walk test, and symptom-limited supine cycle exercise test with simultaneous echocardiography and right heart catheterization will be performed 1-3 weeks after AMI. Subsequently patients will be randomized on the day of exercise test to receive LCZ696 100 mg twice daily or, which will be increased to 200 mg twice daily after 2 weeks if tolerated or matching placebo. After 6 months treatment invasive hemodynamic stress test with simultaneous echocardiography will be repeated. The study will be considered complete with regard to the primary study endpoints after all subjects enrolled have completed their 6 month follow-up.
 |
| Informed consent | 
The study will be conducted according to national and international legislation. Patients will be enrolled after obtaining written informed consent.
 |

3 Study Rationale:

3.1 Diastolic dysfunction after AMI:

Left ventricular (LV) systolic or diastolic dysfunction following acute myocardial infarction (AMI) is common with only 25-33% of the patients having an entirely normal LV function. Based on echocardiographic examinations an estimated 25% of all patients will present with apparently normal systolic function based on LV ejection fraction but diastolic dysfunction based on Doppler echocardiographic criteria (1).

Direct or indirect measurements of increased LV filling pressure is well-established independent risk factor for mortality and morbidity after AMI. Several recent studies have demonstrated that Doppler echocardiographic indices suggestive of increased LV filling pressure and increased pulmonary arterial pressure are associated with excess mortality and morbidity after AMI (2-4). The causal mechanism behind the increased mortality and morbidity due to diastolic dysfunction in patients with preserved systolic function is however poorly understood. Recent data from our group have demonstrated that the underlying pathophysiological response to physical stress in these patients is characterized by a disproportionate increase in LV filling pressure to maintain adequate perfusion (cardiac output) thus suggestive of an upward shift of the pressure volume relationship with increased LV chamber stiffness possibly due to increased myocardial fibrosis (5). Furthermore, this condition is also characterized by an impaired natriuretic and renal endocrine response to acute volume expansion. Thus the pathophysiological characteristics of this condition closely resamples that of heart failure with preserved ejection fraction (6-7).

The optimal management of this group of post-AMI patients is however incompletely understood.

3.2 LCZ696

LCZ696 is a combination drug consisting of two antihypertensives, valsartan and sacubitril. Valsartan acts by blocking the angiotensin II receptor type 1 and thereby causes vasodilation and increases excretion of sodium and water via the kidneys by attenuating aldosterone production. Sacubitril is a prodrug that is activated to an active metabolite (LBQ657) that acts by inhibiting the enzyme neprilysin (8). Neprilysin is responsible for the degradation of natriuretic peptides released from the LV and left atrium in response to increased wall stress and myocyte stretch and act by attenuating the deleterious effects of volume and pressure overload on the heart, a protective mechanism that have been suggested to be deficient in early stage of heart failure with preserved LVEF (9). Augmentation of these mechanisms likely at least partly explain the beneficial effect on outcome of ARNi in heart failure with reduced LVEF that recently was found in the PARADIGM-HF trial, where angiotensin receptor – neprilysin inhibition (ARNi) compared with enalapril treatment was associated with a risk reduction of 20% of composite primary endpoint death and hospitalization for heart failure (10). In patients with heart failure and preserved ejection fraction ARNi has been demonstrated to have a beneficial effects on natriuretic peptides and left atrial remodeling in a clinical Phase II trial (11). Furthermore, recent experimental data also suggest ARNi attenuated cardiac remodeling and dysfunction after experimental AMI in rodents and importantly inhibit cardiac fibrosis in experimental AMI, as well as in vitro beyond that achieved by stand-alone angiotensin receptor blockade (12).

Thus in theory LCZ696 may possess several beneficial properties that may improve hemodynamics and cardiac remodeling in patients with diastolic dysfunction after AMI.

4 Hypothesis:

LCZ696 compared with placebo will improve central hemodynamics (reduce pulmonary capillary wedge pressure (PCWP)), and increase cardiac index (CI) during exercise in patients with diastolic dysfunction after AMI. A beneficial effect that is attributed to improved cardiac remodeling (attenuation of cardiac fibrosis).

5 Objectives:

The main objective of this study is to assess the effect of angiotensin–neprilysin inhibition on central hemodynamics, myocardial structure and myocardial function in patients with a recent AMI and Doppler echocardiographic signs of diastolic dysfunction and preserved systolic function.

5.1 Primary objective:

To assess the effect of 6 months treatment with LCZ696 compared with placebo on ratio of PCWP/CI during exercise in patients with a recent AMI and Doppler echocardiographic signs of diastolic dysfunction and preserved systolic function.

5.2 Secondary objectives:

To assess the effect of 6 months treatment with LCZ696 compared with placebo in patients with a recent AMI and Doppler echocardiographic signs of diastolic dysfunction and preserved systolic function on:

1. Cardiac fibrosis assessed on cardiac magnetic resonance imaging,
2. The ST2 cardiac biomarker
3. Left atrial size and function
4. MR-proANP and NT-proBNP
5. Diastolic dysfunction assessed by Doppler echocardiography

5.3 Primary endpoint:

Ratio of pulmonary capillary wedge pressure to cardiac index at peak exercise after 26 weeks treatment with LCZ696 or placebo.

5.4 Secondary endpoints:

1. Amount of hyperenhancement on cardiac MRI using a semiquantitative assessment of late gadolinium hyperenhancement in a 17 segment model of the LV.
2. ST2 concentration at rest.
3. Left atrial volume by echocardiography and left atrial emptying fraction by echocardiography at rest.
4. MR-proANP and NT-proBNP concentration at rest.
5. Proportion of patients with moderate or severe diastolic dysfunction at rest.

6 Methodology:

The ARNiAMI study is a prospective, multicenter, randomized, double blind clinical trial to evaluate the efficacy, of LCZ696 97/103 mg BID versus matching placebo in subjects aged 50 years or older with a recent documented AMI, diastolic dysfunction and LVEF $\geq 45\%$ on cardiac physiology and myocardial fibrosis. Patients who meet the study inclusions and none of the exclusion criteria will after signing an Ethics Committee approved Informed Consent Form, be asked to undergo baseline procedures for the study.

Patients will be randomized in a 1:1 double-blind trial to receive LCZ696 or matching placebo using a computer-generated randomization schedule. Randomization will be stratified by PWCP at rest. Production of study medication, matching placebo, packing and handling of study medication will be performed by Sygehusapotek Fyn. Study medication will be delivered to the participating centers in blinded containers. Containers will be labeled with a unique identification number. Randomization will be performed by the investigator and a randomization number is assign to the patient. When dispensing study medication container ID's is requested from Sygehusapotek Fyn via E-mail. The randomization codes will be kept in sealed envelopes with the Trial Master file and will not be opened before the study has ended. The randomization schedule will also be available through a password protected online form. In case of emergent need for unblinding the coordinating investigator will be contacted pr. telephone and treatment allocation is unblinded either through the online form (with a dedicated user for this purpose with strict logging) or sealed envelopes. Compliance will be assessed using pill count.

The study will be performed according to ICH-GCP. The ethics Committee for the Region of Southern Denmark will be applied for ethical approval and the study will be registered at ClinicalTrials.gov. All patients will provide written informed consent.

6.1 Justification of key elements of study design:

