6.1.1 Selection of endpoints

A key pathophysiological element of diastolic dysfunction and heart failure with preserved ejection fraction is the inability to increase cardiac output without concomitant excessive increase in LV filling pressure during physical strain. Thus the ratio between LV filling pressure to cardiac output will be abnormally increased during exercise. In many patients filling pressure will be normal or mildly elevated at rest where cardiac output will be normal. Thus resting assessment will often be misleadingly normal in these patients where as evaluation during exercise will uncover the pathophysiology (5,6). By combining filling pressure and cardiac output it will be possible indirectly to assess changes in the pressure volume relationship of the LV which not would be the case if either PCWP or cardiac index alone were chosen.

Cardiac MRI with late gadolinium enhancement is a useful tool for detection of myocardial fibrosis, based on differences in the volume of distribution of gadolinium (13). Although the method is especially well suited to detect the presence of fibrosis in the myocardium in ischemic cardiomyopathy, it may also detect myocardial fibrosis in a wide variety of non-ischemic cardiomyopathies. Modification of myocardial fibrosis will provide an important pathophysiological link between assessment of central hemodynamics during exercise and effects of ARNi. In addition cMRI provides detailed information on cardiac structure thus it will provide very precise data on LV remodeling (LV volumes and LV mass) and LA remodeling. Thus provide important explanatory data.

ST2 is a member of the interleukin 1 receptor family. The ST2 gene is highly expressed by cardiomyocytes and fibroblasts when strained in this setting ST2L becomes receptive for interleukin-33 which has antihypertrophic and antifibrotic effects (14). Thus ST2 concentration reflects cardiac

remodeling and myocardial fibrosis. After AMI ST2 has been demonstrated to predict prognosis (15) and be associated with presence of heart failure. Differences in ST2 concentrations between groups will provide insights into the mechanisms of the potential effect of ARNi.

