15.2 Analysis of primary endpoint

Primary endpoint, PCWP/CI ratio, will be analyzed using ANCOVA with treatment as fixed effect factor. Additionally, the baseline value of the corresponding variable may be included as a covariate if appropriate. The estimated treatment effect and the corresponding two-sided 95% confidence interval will be provided.

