1.2 Analysis of primary endpoint

Primary endpoint, PCWP/CI ratio, will be analyzed using ANCOVA or mixed effects models with treatment as fixed effect factor with the intention-to-treat principle. Additionally, the baseline value of the corresponding variable may be included as a covariate if appropriate. The estimated treatment effect and the corresponding two-sided 95% confidence interval will be provided.

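### Randomisation is stratified by resting PCWP, but the primary model does not name the stratum, so the 95% CI can be wider than the design warrants

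*Protocol*

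**What the plan says.** Protocol section 6 (Methodology) describes a 1:1 computer-generated schedule and adds "Randomization will be stratified by PWCP at rest" (PWCP is evidently PCWP). It gives no cut-point, number of strata or block size, and does not say whether allocation is blocked.

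The primary endpoint (protocol 5.3) is "Ratio of pulmonary capillary wedge pressure to cardiac index at peak exercise after 26 weeks treatment with LCZ696 or placebo".

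- Protocol 15.2: the endpoint "will be analyzed using ANCOVA with treatment as fixed effect factor".
- SAP 1.2: the endpoint "will be analyzed using ANCOVA or mixed effects models with treatment as fixed effect factor".
- Both add that "the baseline value of the corresponding variable may be included as a covariate if appropriate". The corresponding variable is the PCWP/CI ratio, not resting PCWP or its stratum.

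The mixed-model wording in the SAP does not rule out a stratum term, but no text in either document prespecifies one.

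**The concern.** Balancing the arms within strata of a prognostic variable removes the between-stratum variation from the true error of the treatment difference. A model without the stratum still counts that variation as residual noise. Its standard error is then too large, its 95% interval covers more than 95% of the time, and its test rejects less than 5% of the time under the null.

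Two conditions are needed: restricted allocation within strata, and a stratum that predicts the outcome. Neither can be confirmed from the documents.

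What is at stake is power in a trial sized for 90 evaluable patients, each asked to undergo two invasive exercise tests. The secondary hypotheses are tested only if the primary one is rejected (protocol 15.3, SAP 1.3), so a conservative primary test also holds those back. Leaving the covariates open also leaves the primary model to be chosen later, and that does not depend on either condition.

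**Working it through.** **Inputs from the documents** (protocol 6.1.3): difference 0.898 (20% of 4.49), standardized difference 0.598, two-sided alpha 0.05, power 80% (written there as beta 0.8), 90 evaluable, 100 enrolled. The table implies SD = 0.898/0.598 = 1.5; the text gives 1.4. I use 1.5 because it is the value that reproduces the plan's 90.

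**Assumptions not in the documents:** two strata, blocks of 4 within stratum, and r, the correlation of resting PCWP with the week-26 ratio, at 0, 0.3, 0.5 and 0.7.

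**1. The plan's sample size.** Per arm, n = 2(1.960 + 0.842)² × 1.5² / 0.898² = 43.8, so 44 per arm and 88 in total. The t-based solution gives 90, and 90/(1 − 0.10) = 100. The stated figures reproduce. With SD 1.4 the totals would be 78 (normal) or 80 (t).

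**2. Treatment-only model, by formula.** The model-based SE is 1.5 × √(4/90) = 0.316. A median split of a normal variable explains R² = r² × 2/π of the outcome variance. With balance within strata the true SE is 0.316 × √(1 − R²), so the SE is overstated by the factor 1/√(1 − R²), and the actual type I error is 2[1 − Φ(1.96/√(1 − R²))].

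| r | R² | SE overstated by | Type I error |
|---|---|---|---|
| 0.3 | 0.057 | 3.0% | 4.35% |
| 0.5 | 0.159 | 9.1% | 3.3% |
| 0.7 | 0.312 | 20.6% | 1.8% |

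**3. Simulation, treatment-only.** 20,000 trials per scenario; noise in the excess SE is about ±1 percentage point. Power is for a true difference of 0.898.

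| Cut | r | Excess SE | Type I error | Power without stratum | Power with stratum |
|---|---|---|---|---|---|
| Median | 0.3 | 3% | 4.4% | 80% | 82% |
| Median | 0.5 | 10% | 3.0% | 82% | 87% |
| Median | 0.7 | 20% | 2.0% | 84% | 92% |
| 80/20 | 0.3 | 2% | 4.7% | 81% | 82% |
| 80/20 | 0.5 | 6% | 3.5% | 82% | 85% |
| 80/20 | 0.7 | 13% | 2.6% | 83% | 90% |

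For the median split, the model-based SEs are 0.316/0.317/0.317 against empirical SDs of 0.308/0.287/0.264. A repeat simulation gave type I error 4.3%/3.7%/2.1% and power 81%/82%/84% without the stratum, 83%/86%/92% with it.

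A separate run set R² directly (50:50 strata). At R² = 0.1/0.2/0.3/0.4 the treatment-only interval covered 96.3%/96.9%/98.0%/98.8%. Its mean width was 1.25/1.25/1.26/1.26, against 1.19/1.12/1.05/0.97 with the stratum.

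**4. Baseline ratio in the model.** This adds two assumed correlations: 0.5 between resting PCWP and the baseline ratio, and 0.6 between the baseline and week-26 ratios (median split).

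| r | Excess SE | Type I error | Power without stratum | Power with stratum |
|---|---|---|---|---|
| 0.3 | 0% | 4.8% | 94% | 94% |
| 0.5 | 3% | 4.2% | 94% | 95% |
| 0.7 | 9% | 3.2% | 95% | 97% |

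The first row is zero for a reason: 0.5 × 0.6 = 0.30, so at r = 0.3 resting PCWP carries nothing beyond the baseline ratio. Over other baseline correlations (0.3 to 0.7), excess SE is 0 to 5% and the power gain 0 to 2 points at r = 0.3 to 0.5. At r = 0.7 they are 3 to 15%, and under 1 to 4 points.

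**5. Where the effect vanishes.** Treatment-only at r = 0: no excess SE, type I error 5.0%, power 80.3% with and without the stratum. Simple randomisation at r = 0.5 and 0.7: excess SE 0 to 0.5%, type I error 4.6 to 5.2%; the CI is valid and only the available precision goes unused.

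**The case against.** The strongest reply is that the large figures belong to a different weakness, the optional baseline covariate. ANCOVA ordinarily carries a covariate, and the next sentence names the candidate, so treatment-only is the worst-case reading. Once the baseline ratio is in, the stratum adds little. A correlation would normally weaken over six months, so r should not exceed the correlation of resting PCWP with the same-day baseline ratio. In a simulation of five such combinations (r from 0.2 to 0.5, 8,000 trials each), the excess SE was −1% to +1% and power moved by at most 0.1 point. Protocol 6.1.1 also points to a modest r, since "resting assessment will often be misleadingly normal in these patients". Finally, the error is conservative, and under blocking the treatment-only power stays at 80% or above.

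Most of this stands, and it limits the size of the point: with the baseline ratio mandatory and r modest, the stratum is worth almost nothing in power. It does not remove the point. The baseline ratio is not mandatory, treatment-only is permitted as written, and the correlations are unknown to the reader of the plan. The five combinations also lie close to the case where resting PCWP adds nothing beyond the baseline ratio, so a null result there is expected.

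**Conclusion.** The concern holds. Neither primary model names the variable on which randomisation is stratified, and the text permits an analysis that ignores it. With blocking and a prognostic resting PCWP, the treatment-only SE is about 3% to 20% too large for r = 0.3 to 0.7 (median split), at a cost of about 2 to 8 points of power. With the baseline ratio included, the excess is about 0 to 9% and the cost about 0 to 2 points under the central assumptions.

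These sizes rest on assumed blocks, cut-points and correlations. The direction does not depend on the particular values: precision is lost, with no bias and no added false-positive risk. The change is worth making because it is nearly free, but validity is not threatened. Confidence in the size is moderate, because r and the allocation scheme are not given.

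**What to change.** In protocol 15.2 and SAP 1.2, prespecify the resting-PCWP randomisation stratum, in the categories used in the randomisation schedule, as a fixed factor in the primary model, next to treatment and the baseline PCWP/CI ratio. State the cut-point and whether allocation was blocked within strata. This covers the primary model only.

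The cost is one line of wording and one degree of freedom per stratum beyond the first. Resting PCWP is measured before randomisation, so no new data are needed, and the r = 0 run shows no power lost when the stratum is not prognostic (80.3% either way).

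The SAP is dated 07022024, the protocol planned the last visit for July 2020, and neither document says whether allocation has been revealed. If it has, report the stratum-adjusted model as a labelled supplementary analysis.
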